1.3 Benefit/risk and ethical assessment

This study will not provide any direct medical benefits to subjects who participate. The major risk for subjects who participate in the study is from adverse events (AEs) induced by ceftaroline or injection site pain, thrombophlebitis, and infection from numerous PK blood sampling and intravenous needle placement.

In the Phase III clinical studies, the overall incidence of adverse drug reactions is low, and comparable among ceftaroline and the comparators. No AE reactions occurred in $>5\%$ of subjects receiving ceftaroline fosamil. The most common adverse reactions occurring in $\geq 4\%$ of the subjects receiving ceftaroline fosamil in the pooled Phase III clinical studies were diarrhoea, nausea, and headache.

Monitoring will be performed according to Good Clinical Practice (GCP)/International Conference on Harmonisation (ICH) guidelines. Safety data will be collected during the study. In addition, there will be complete data gathering (eg, through questionnaires) to allow proper safety evaluation on the following events, which are currently classified as important potential risks for ceftaroline in the global and European Union Patient Risk Management Plan, if they would occur in the study: haemolytic anaemia, drug-induced liver disease, renal impairment, and seizures.

Clinical laboratory, electrocardiogram (ECG), and vital signs results for subjects in this study will be monitored and clinically significant abnormalities will be reviewed and assessed by the investigator.

The sponsor will immediately notify the principal investigator of important safety data (eg, toxicology, absorption, distribution, excretion, teratology) that becomes available during the study.

2. STUDY OBJECTIVES

2.1 Primary objective

To characterise the PK of ceftaroline after intravenous infusion of ceftaroline fosamil in patients with ESRD and a matched control population with normal renal function and to characterise the clearance of ceftaroline by haemodialysis.

2.2 Secondary objectives

1. To evaluate the safety and tolerability of a single intravenous infusion of ceftaroline fosamil in patients with ESRD undergoing intermittent haemodialysis
2. To characterise the PK of ceftaroline fosamil (the prodrug of ceftaroline) and ceftaroline M-1 (the microbiologically inactive metabolite of ceftaroline) after intravenous infusions of ceftaroline fosamil, in patients with ESRD undergoing intermittent haemodialysis and a matched control population with normal renal function

3. STUDY PLAN AND PROCEDURES

This clinical study protocol (CSP) has been subject to a peer review according to AstraZeneca standard procedures.

3.1 Overall study design and flow chart

This is an open-label, nonrandomised, Phase I, single dose study to assess the PK, safety, and tolerability of ceftaroline in male and female patients with ESRD requiring intermittent haemodialysis (Group 1). A group of healthy male and female volunteers with normal renal

function and similar demographics (Group 2) will be recruited to provide within-study reference data.

The study will be conducted at 1 study centre in the United Kingdom. A minimum of 8 healthy volunteers and 8 patients with ESRD will be enrolled.

Group 1 will consist of up to 8 patients with ESRD who will participate in 2 treatment periods (separated by a washout of at least 1 week) in order to study these patients under haemodialysis and nondialysis conditions. Group 2 will consist of up to 8 healthy volunteers who will participate in 1 treatment period. Approximately 16 subjects will be screened and enrolled in order to have at least 6 subjects in each group completing the study.

[figure not shown]
The study will consist of a screening period (Day -28 to Day -2), residential period (2 treatment periods, Day -1 to Day 3 [Group 1] or 1 treatment period, Day -1 to Day 2 [Group 2]), and a follow-up period (7 to 10 days after discharge from the study centre).

Group 1 (patients with ESRD)

After screening, eligible patients will be admitted to the study centre for Period 1 on Day -1 and will receive a single intravenous dose of 200 mg ceftaroline fosamil infused over 1 hour on Day 1. The infusion will start at least 1 hour after the end of a haemodialysis session and 48 hours before the next scheduled haemodialysis. Blood samples will be collected for up to 48 hours after the start of the infusion for the determination of ceftaroline fosamil, ceftaroline, and ceftaroline M-1. The patients will remain in the study centre until the completion of the study procedures on Day 3.

After a washout of at least 1 week, patients will be admitted to the study centre on Day -1 for Period 2 and will receive a single intravenous dose of 200 mg ceftaroline fosamil infused over 1 hour on Day 1, prior to the haemodialysis session. Haemodialysis will then start 15 minutes after the end of the infusion, within a ± 5 minutes time window. Samples of blood and dialysate will be collected for up to 48 hours after the start of the infusion for the determination of ceftaroline fosamil, ceftaroline, and ceftaroline M-1. Blood samples will also be collected at specified time points for haematocrit and endogenous markers including blood urea nitrogen and creatinine. Patients will remain in the study centre until the completion of the study procedures on Day 3. The study design for Group 1 is presented in Figure 1.

[figure not shown]
Figure 1 Study design for Group 1

Group 2 (healthy volunteers)

After screening, eligible healthy volunteers will be admitted to the study centre on Day -1 and will receive a single intravenous dose of 600 mg ceftaroline fosamil infused over 1 hour on Day 1. Blood will be collected for up to 24 hours after the start of infusion for the determination of ceftaroline fosamil, ceftaroline, and ceftaroline M-1. The healthy volunteers will remain at the study centre until the completion of the study procedures on Day 2. The study design for Group 2 is presented in Figure 2.

Figure 2 Study design for Group 2

Throughout the treatment periods, subjects will be monitored for safety and blood samples for the PK evaluation will be collected.

The schedule of assessments and the PK sampling time points are provided in [Table 2](#) and [Figure 3](#), respectively.

Table 2 Schedule of assessments

Assessment	Screening	Residential period/ treatment period ⁿ				Follow-up
	Day -28 to -2	Day -1	Day 1	Day 2	Day 3	7-10 days after discharge
Informed consent ^a	X					
Inclusion/exclusion criteria	X	X				
Demographics	X					
Medical, surgical, and smoking history	X					
Luteinising hormone/follicle-stimulating hormone ^b	X					
Estimated creatinine clearance ^c	X	X		X ⁱ	X ⁱ	
Hepatitis B, hepatitis C, and HIV	X					
Alcohol and urine drug screen	X	X				
Clinical chemistry and haematology ^b	X	X			X	X
Urinalysis/urine microscopy ^d	X	X				X
Pregnancy test ^e	X	X				X
Physical examination		X			X	
Brief physical examination						X
Height, weight, and BMI calculation ^f	X	X				X
12-Lead electrocardiogram ^g	X	X				X
Admission to study centre		X				
Intravenous infusion of investigational product ^h			X			
Discharge from the study centre ⁱ				X	X	
Haemodialysis/dialysate collection ^j			X			
Vital signs ^k	X	X	X	X	X	X
Blood collection for pharmacokinetics ^l			X	X	X	
Haematocrit blood sampling for Group 1/Period 2 only ^l			X			
Blood urea nitrogen/creatinine blood sampling during dialysis for Group 1/Period 2 only ^l			X			
Prior and concomitant medication recording	X	X	X	X	X	X

Assessment	Screening	Residential period/ treatment period ⁿ				Follow-up
	Day -28 to -2	Day -1	Day 1	Day 2	Day 3	7-10 days after discharge
Adverse event/serious adverse event recording ^m	X	X	X	X	X	X

- ^a Informed consent will be collected before any study-specific procedures are performed.
- ^b The healthy volunteers in Group 2 will fast for 4 hours before the clinical laboratory evaluations at screening and during the residential period. Fasting is not required for the follow-up visit. Luteinising hormone and follicle-stimulating hormone will be measured to determine menopausal status at the screening visit.
- ^c Creatinine clearance will be estimated using the Cockcroft-Gault formula at the screening visit, admission to the study centre, and at discharge from the study centre.
- ^d A urine sample for urinalysis and microscopy will be collected, if possible, along with the other clinical laboratory evaluations.
- ^e A serum pregnancy test will be performed for all females. If positive, the subject will be excluded from participation in the study.
- ^f Height and weight will be evaluated at the screening visit and BMI will be calculated. Only weight will be evaluated at all other visits.
- ^g A 12-lead electrocardiogram will be performed after the subject has rested in the supine position for 10 minutes.
- ^h Patients in Group 1 will each receive 2 single intravenous infusions of 200 mg ceftaroline fosamil, infused over 1 hour (1 infusion in each treatment period). Healthy volunteers in Group 2 will each receive 1 single intravenous infusion of 600 mg ceftaroline fosamil, infused over 1 hour.
- ⁱ Subjects will be discharged from the study centre after the completion of all study-related procedures. This will be Day 3 for Group 1 and Day 2 for Group 2.
- ^j Only applicable for Group 1, Period 2. The patients will start their scheduled haemodialysis 15 minutes after the end of the 1-hour infusion (within a ± 5 minutes time window). Dialysate will be collected over 1-hour intervals throughout the entire haemodialysis session as shown in [Figure 4](#).
- ^k Supine blood pressure and pulse rate will be evaluated after the subject has rested in the supine position for at least 10 minutes. If possible, the same arm and the same make and model of equipment should be used for each evaluation. During the residential period, predose blood pressure and pulse rate will be evaluated within 60 minutes before the start of the infusion.
- ^l Blood samples will be collected at the time points provided in [Figure 3](#) and [Figure 4](#).
- ^m Serious adverse events will be collected from the time of informed consent up to the follow-up visit. Adverse events will be collected from Day 1 until the follow-up visit.
- ⁿ Group 1 will have 2 residential periods/treatment periods (Period 1 and Period 2) and Group 2 will have 1 residential period/treatment period (Period 1).

BMI: body mass index; HIV: human immunodeficiency virus.

Figure 4 Time schedule for pharmacokinetic assessments in Group 1/Period 2

Study day	Administration of the investigational product	Protocol time (after the start of the infusion)	Group 1/Period 2				
			Haemo-dialysis	PK blood sample	Haemato-crit blood sample	BUN/creatinine blood sample	Dialysate collection ^d
1	Start of infusion ↓ ↓ End of infusion	Predose ^a 0		X	X		
		20 minutes		X			
		40 minutes		X			
		60 minutes		X ^b			
		65 minutes		X			
		75 minutes	Start	X ^c			X ^f
		90 minutes	↓	X ^{d,e}		X ^{d,e}	↓
		2.25 hours	↓	X ^{d,e}		X ^{d,e}	X ^f
			↓				↓
		3.25 hours	↓	X ^{d,e}		X ^{d,e}	X ^f
			↓				↓
		4.25 hours	↓	X ^{d,e}		X ^{d,e}	X ^f
			↓				↓
		5.25 hours	End	X ^{d,e}			X ^f
2		8 hours		X	X		
		12 hours		X			
		24 hours		X			
		36 hours		X			
3		48 hours		X			

^a The predose samples will be collected within 1 hour before the start of the infusion.

^b End of infusion samples will be collected within 2 minutes of the end of the infusion.

^c Haemodialysis to start 15 minutes after the end of the infusion, within a ±5 minutes time window; the 75 minute PK sample will be collected just prior to the start of the haemodialysis.

^d All blood samples collected during and surrounding the haemodialysis session will be collected from both predialyser and postdialyser lines. At each timepoint, the pre- and postdialyser samples should be collected as close as possible in the following sequence: predialyser PK, predialyser BUN/creatinine, postdialyser PK, and post dialyser BUN/creatinine samples. The postdialyser sample should be collected within 1 minute of the respective predialyser sample.

^e The blood samples during haemodialysis session, including protocol times 90 minutes, 2.25 hour, 3.25 hour, and 4.25 hour, should be collected at 15 minutes, 1 hour, 2 hours, and 3 hours after the start of

haemodialysis, respectively; the 5.25 hour (4 hours after start of haemodialysis) samples must be collected just at the end of the haemodialysis session.

- f Dialysate will be collected in appropriate containers over 1 hour intervals throughout the entire (approximately 4 hours) haemodialysis session (including, 0 to 1, 1 to 2, 2 to 3, 3 to 4 hours after the start of haemodialysis). The blood flow, dialysate flow rate, dialysate volume, type of dialysis membrane, and the make and model of the dialyser will be recorded. The entire dialysate will be collected, its volume recorded, and the primary and backup samples retained for analysis of ceftaroline and ceftaroline M-1 concentrations.

BUN: blood urea nitrogen; PK: pharmacokinetic.

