7. Stable physical condition, consistent with ESRD, based on the results of the medical history, vital signs, 12-lead ECG, and clinical laboratory evaluations performed within 3 weeks of the first investigational product administration. As a result of renal impairment or underlying disease, certain laboratory parameters may be outside the normal reference ranges
8. CrCL by Cockcroft-Gault of <15 mL/min **or on haemodialysis**
9. Patients who require haemodialysis 3 to 4 times per week and are receiving the same dialysis regimen for at least 1 month before screening
10. Haematocrit level higher than 30% at screening and baseline for each treatment period
11. Concomitant medications to treat underlying diseases or medical conditions related to renal insufficiency are allowed, except when specifically excluded by name or pharmacological class

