6.3.5 Laboratory safety assessment

Blood and urine samples for determination of clinical chemistry, haematology, and urinalysis will be taken at the times indicated in [Table 2](#). The safety samples will be analysed by the laboratory at the study centre. The date and time of sample collection will be recorded in the CRF.

The safety laboratory variables to be measured are provided in [Table 4](#).

Table 4 Safety laboratory variables

Clinical chemistry (serum)	Haematology (blood)
Albumin	Haemoglobin
Alkaline phosphatase	Leukocytes
Aspartate aminotransferase	Absolute leukocyte differential count
Alanine aminotransferase	Platelet count
Total bilirubin	
Total calcium	Urinalysis
Creatinine	Glucose
Glucose	Haemoglobin
Potassium	Protein
Sodium	
Serology	Other
Human immunodeficiency virus ^a	Follicle-stimulating hormone (females only) ^a
Hepatitis B and C ^a	Luteinising hormone (females only) ^a
	Pregnancy test (females only)
	Creatinine clearance

^a At screening only.

The healthy volunteers in Group 2 will fast for 4 hours prior to the safety laboratory assessments at screening and during the residential period. Fasting is not required for the follow-up visit.

Luteinising hormone and FSH will be measured in females to determine menopausal status. A serum pregnancy test will be performed for females at screening, Day -1, and follow-up.

Urine will be tested for the following drugs of abuse at screening and Day -1: amphetamines, barbiturates, tricyclic antidepressants, cocaine, methadone, morphine, tetrahydrocannabinol, and opiates. Subjects will be screened for alcohol at screening and Day -1. If a subject tests positive for any of these screening tests, he/she will be excluded from the study.

A urine sample for urinalysis and microscopy will be collected, if possible, together with other clinical laboratory evaluations.

Creatinine clearance will be estimated using the Cockcroft-Gault formula at screening, admission, and discharge:

$$\text{Males: CrCL (mL / min)} = \frac{(140 - \text{age}) \times (\text{kg body weight})}{(0.814 \times \text{micromol / L serum creatinine})}$$

$$\text{Females: CrCL (mL / min)} = \frac{(140 - \text{age}) \times (\text{kg body weight}) \times 0.85}{(0.814 \times \text{micromol / L serum creatinine})}$$

where age is expressed in years, weight in kg, and serum creatinine in $\mu\text{mol/L}$.

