7. BIOLOGICAL SAMPLING PROCEDURES

7.1 Volume of blood

The total volume of blood that will be drawn from each subject in this study is presented in Table 5.

Table 5 Volume of blood to be drawn from each subject

Assessment		Sample volume (mL) ^a	No. of samples (Group 1)	No. of samples (Group 2)	Total volume (mL) (Group 1)	Total volume (mL) (Group 2)
Safety	Clinical chemistry	2	6	3	12	6
	Haematology	2	6	3	12	6
	Serology	3.5	1	1	3.5	3.5
Pregnancy test, luteinising hormone, and follicle-stimulating hormone ^b		3.5	3	4	10.5	14
Pharmacokinetics		4	37 (32 +5 ^c)	14	148	56
Haematocrit (Group 1/Period 2 only)		2	2	NA	4	NA
Blood urea nitrogen and creatinine (Group 1/Period 2 only)		2	10 (5 + 5 ^c)	NA	20	NA
Total					210	85.5

^a If a cannula is used, an additional 1 mL of blood will be collected to flush the cannula at each sample time point.

^b Females only.

^c Samples collected from postdialyser line.

NA: not applicable.

The number of samples collected, as well as the volume required for each analysis may be changed during the study. However, the maximum volume to be drawn from each subject will not exceed 450 mL, ie, the same volume as would be drawn during a regular blood donation.

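### Group 2 leaves on Day 2, but in-house post-dose chemistry, haematology and full physical examination are marked only on Day 3, so its required discharge creatinine clearance has no scheduled serum creatinine

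*Protocol*

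**What the plan says.** **Discharge.** Group 2 stays from Day -1 to Day 2. Section 3.1 says: "The healthy volunteers will remain at the study centre until the completion of the study procedures on Day 2". Footnote i of Table 2 repeats the split by group: "This will be Day 3 for Group 1 and Day 2 for Group 2".

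**Laboratory tests and examination.** In Table 2 the chemistry and haematology row is marked at screening, Day -1, Day 3 and follow-up, with nothing on Day 1 or Day 2. The full physical examination is marked on Day -1 and Day 3. The row "Brief physical examination" is marked at follow-up only, 7 to 10 days after discharge.

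**Creatinine clearance.** This row is marked at screening, Day -1, Day 2 and Day 3, the last two carrying footnote i. Footnote c asks for it at screening, admission and discharge. Section 6.3.5 says the same: "Creatinine clearance will be estimated using the Cockcroft-Gault formula at screening, admission, and discharge". The formula there uses serum creatinine, which Table 4 lists under clinical chemistry.

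**Blood budget.** Table 5 in Section 7.1 ("Volume of blood to be drawn from each subject") counts 6 chemistry and 6 haematology samples for Group 1 and 3 of each for Group 2.

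**Haematocrit.** Inclusion criterion 10 requires "Haematocrit level higher than 30% at screening and baseline for each treatment period". Table 4 does not list haematocrit, and the Table 2 row reads "Haematocrit blood sampling for Group 1/Period 2 only".

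**The concern.** The creatinine clearance and discharge rows of Table 2 were split so that Day 2 serves Group 2 and Day 3 serves Group 1. The chemistry/haematology and physical examination rows were not. A site following the table literally would discharge a healthy volunteer on Day 2 owing a discharge clearance with no creatinine to put into it.

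The same omission leaves Group 2 without a laboratory result or examination between dosing and follow-up. Several of the effects the protocol itself names show up mainly in blood tests. Table 1 lists raised creatinine and transaminases, thrombocytopenia and anaemia, and Section 1.3 names haemolytic anaemia, drug-induced liver disease and renal impairment as important potential risks. A short-lived change after the infusion could have resolved by follow-up.

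Adverse event recording does not fully cover this. Under Section 6.3.3, a worsening in a protocol-mandated test without symptoms becomes an adverse event only if it meets a seriousness criterion or leads to stopping treatment. A test that is not taken cannot show the worsening at all.

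**Working it through.** No sample-size or power calculation bears on this. The check is a count of visits against Table 5.

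**Step 1. Reproduce Table 5 from Table 2 (chemistry; haematology is identical).**

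| Visit | Group 1 | Group 2 |
|---|---|---|
| Screening | 1 | 1 |
| Day -1 | 2 (two periods) | 1 |
| Day 3 | 2 (two periods) | 0 (already discharged) |
| Follow-up | 1 | 1 |
| Sum | 6 | 3 |
| Table 5 | 6 | 3 |

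Both counts match. A Group 2 discharge sample would make the sum 1 + 1 + 1 + 1 = 4, which is not what Table 5 states. Two tables therefore agree that no Day 2 chemistry or haematology is planned, and a mark lost in reading the PDF is an unlikely explanation.

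**Step 2. Reproduce the blood volumes (mL).**

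- Group 1: 12 + 12 + 3.5 + 10.5 + 148 + 4 + 20 = 210, as stated.
- Group 2: 6 + 6 + 3.5 + 14 + 56 = 85.5, as stated.

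**Step 3. Look for another source of a Day 2 creatinine.**

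- The separate creatinine samples in Table 2 are taken during dialysis in Group 1, Period 2 only.
- The Day -1 creatinine could be put into the formula on Day 2. But Section 6.3.6 measures weight only at screening, Day -1 and follow-up, so creatinine and weight would both be the admission values. The result would repeat the admission clearance.

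**Step 4. Time to the first post-dose laboratory value in Group 2.** Dosing is on Day 1 and discharge on Day 2, about 1 day later. Follow-up is 7 to 10 days after discharge. Hence 1 + 7 = 8 to 1 + 10 = 11 days after dosing.

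**Step 5. Post-dose assessments that Group 2 does have.**

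- In house: vital signs, adverse events and concomitant medication on Days 1 and 2.
- At follow-up: chemistry, haematology, urinalysis, ECG, vital signs and the brief examination. Compared with the full examination in Section 6.3.6, the brief one leaves out the thyroid, musculoskeletal and neurological assessments.

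**Step 6. Haematocrit (separate).** Criterion 10 sets three time points: screening, Period 1 baseline and Period 2 baseline. Figure 4 and Table 5 give two samples, predose and 8 hours, both in Period 2. Only the Period 2 baseline has a named test, so 2 of the 3 time points have none. A haematology tube is drawn at screening and on each Day -1, so no blood draw is missing, only the listed variable.

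**The case against.** The strongest reply is that this is a clerical slip with little consequence. Table 2 orders a Day 2 clearance, so a site would probably draw the creatinine anyway. Table 2 omits other marks: Section 6.2.1 asks for a complete physical examination at screening and the table shows none. Table 5 allows sample numbers to change, and its pregnancy and hormone row is odd (3 for Group 1, 4 for Group 2, although Group 1 has the extra Day -1 visit). The secondary safety objective is confined to patients with ESRD, and Group 2 is there as a PK reference. The 600 mg dose is described as established, and Section 1.1 reports no safety concerns after single doses of 1500 and 2000 mg. Section 6.3.5 lets the investigator add laboratory tests for safety.

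Much of this stands. It limits the consequence but does not remove the contradiction. The chemistry and haematology rows of Table 5 do match Table 2, so the documents read together plan no Day 2 draw, and a permission to add tests does not schedule one.

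Three stronger readings are tempting and are not supported:

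- *Group 2 has no in-house post-dose safety data.* It does: vital signs and adverse events on Days 1 and 2.
- *The safety tables of the two groups are made non-comparable.* Section 12.2 plans listings and descriptive summaries, with no between-group safety test. Laboratory values in ESRD are expected to be abnormal anyway. A Group 2 draw at 24 hours would still not match Group 1's at 48 hours.
- *The haematocrit criterion cannot be verified.* The blood is drawn; the variable is simply not listed.

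**Conclusion.** The point holds as an inconsistency between Table 2, its footnotes c and i, Section 6.3.5 and Table 5. Followed as written, the plan gives none of the 8 planned Group 2 subjects a valid discharge creatinine clearance. It also gives them no in-house post-dose chemistry, haematology or physical examination, and no post-dose laboratory value until about 8 to 11 days after dosing. This assumes that the Table 2 marks are as read, which Table 5 supports, and that sites draw only what is scheduled.

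The effect is on safety documentation. The primary PK objective is untouched, and no eligibility decision or stated analysis depends on the discharge clearance. It is worth correcting because the plan requires a value it does not supply and the correction is cheap. The haematocrit mismatch is separate and minor.

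**What to change.** **Main change.** Reconcile the four places so that the post-dose chemistry/haematology and physical examination rows of Table 2 carry footnote i, as the creatinine clearance row already does: Day 3 for Group 1, Day 2 for Group 2. Draw the Group 2 blood with the 24-hour PK sample. State that the discharge clearance uses that creatinine, and which weight it uses. In Table 5, change the Group 2 chemistry and haematology counts from 3 to 4.

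**Cost.** One 2 mL chemistry and one 2 mL haematology sample per healthy volunteer: 85.5 + 2 + 2 = 89.5 mL, against the 450 mL cap. Chemistry alone would give 87.5 mL. It adds no visit and no extra sampling time. The rest is one examination before discharge and edits to two tables.

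**If no Day 2 test is intended.** The Day 2 clearance mark should be removed, and footnote c and Section 6.3.5 limited to Group 1. That would make the text consistent but leave the 8 to 11 day gap, so it should be stated as a deliberate choice.

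**Haematocrit.** Bring inclusion criterion 10 into line with Tables 2, 4 and 5, for example by listing haematocrit in the Table 4 haematology panel. The tube is already drawn at screening and on each Day -1, so this needs no extra blood.
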